To enhance recruitment, we will do the following: discuss the study directly with partners to address any questions/concerns; frame weight loss as a couples' issue in recruitment materials; emphasize potential benefits of the intervention and outcome assessments to partners; offer sessions at different times of day; and offer two sessions that address communication to couples in the patient-only arm following the 24-month assessment. If partners no longer wish to receive intervention, then we will retain patients in the intervention (intent-to-treat analyses). If patients no longer wish to receive the intervention, then partners will no longer receive the intervention either. In such cases, we will ask patients (and partners) to return for outcome assessments, as we have done in our previous trials. Other efforts to maximize retention for outcome assessments include: administer the ASA24 online; e-mail/text reminders one week prior to the beginning of each window; place telephone calls and mail letters if participants are non-responsive to electronic reminders; compensate patients and partners \$40 each for completed interim assessments; and increase payments for the final assessment (\$60 each), as we did in the

MAINTAIN trial. In the MAINTAIN trial, 85% of patients returned for final assessments; in the CouPLES trial, 88% of patients and 70% of spouses did.(42, 50)

No participant will be excluded on the basis of race or sex. There have been mixed findings regarding the moderating role of sex in couples-based weight loss interventions. Failure to balance arms with respect to sex could, therefore, affect outcomes. Sex is explicitly accounted for in the study design in that it is a stratification variable. This variable, along with the other stratification variables of patient BMI and partner BMI, will be included in the statistical models for the primary outcome of weight, secondary outcomes of diet and physical activity, and mediation analyses.

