### 9.2.1 Screening visit:

The screening visit will occur up to 8 weeks prior to the first group intervention visit. The following measurements will be obtained at screening by the WREN Research Coordinators:

- **Medical history and demographics:** age, race, ethnicity, gender and birth sex, insurance status, financial stress, education, smoking status, alcohol use, illicit drug use, employment status, previous weight loss attempts, history of heart disease, diabetes, cancer, liver disease, and hypertension.
- **Body weight** will be obtained using a calibrated digital scale in light clothing, with shoes removed.
- **Height** will be determined without shoes using a portable or wall-mounted stadiometer.
- **BMI.** The weight and height measures will be used to calculate BMI (weight in kilograms divided by height in meter squared; kg/m^2).
- **Dietary intake** will be assessed using the Automated Self-Administered 24-hour dietary recall (ASA24).(51, 52) Patients will receive training to use the website during the screening visit and may call study staff to ask for assistance. Electronic messages via text and/or e-mail will be sent to notify participants on one randomly determined weekend day and one weekday during the measurement window to complete an unscheduled 24-hour recall. Patients who do not comply within 24 hours will be sent notifications to complete recalls on other dates within the window.
- **Physical activity** will be assessed with FitbitTM watches. Patients will be given their FitbitTM and download the FitbitTM application at their screening visit, along with instructions on how to use and wear it. They will be sent a text and/or e-mail reminder about when to start wearing it continuously for 7 days. Patients will be instructed to return the FitbitTM to the study team if they do not attend the first group session.

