**Couples' communication sessions (patient-only arm)**

Following the 24-month outcome assessment, we will offer sessions 1 and 2 from the partner-assisted intervention to couples in the patient-only arm.

**9.2.3 Follow up:****Table 7.** Acceptable Window for Study Visits (including weekends)

Visit	Window	Activities
Screening visit	Up to 8 weeks prior to first group session	Informed consent, medical history/demographics, weight, dietary intake, physical activity, transformation of motivation, couples' efficacy, outcome efficacy, use of communal coping, social support for diet and physical activity, brief pain inventory-short form, COVID-19
Month 0	1st group session (0-8 weeks post screening visit)	Baseline weight is recorded, randomization status is revealed to participant.
Month 3	+/- 14 days from target assessment date	Transformation of motivation, couples' efficacy, outcome efficacy, use of communal coping, social support for diet and physical activity, COVID-19
Month 6	+/- 14 days from target assessment date	Weight, dietary intake, physical activity, transformation of motivation, couples' efficacy, outcome efficacy, use of communal coping, social support for diet and physical activity, brief pain inventory-short form, weight loss methods, COVID-19
Month 9	+/- 14 days from target assessment date	Transformation of motivation, couples' efficacy, outcome efficacy, use of communal coping, social support for diet and physical activity, COVID-19
Month 12	+/- 14 days from target assessment date	Weight, dietary intake, physical activity, transformation of motivation, couples' efficacy, outcome efficacy, use of communal coping, social support for diet and physical activity, brief pain inventory-short form, weight loss methods, COVID-19

Month 15	+/- 14 days from target assessment date	Transformation of motivation, couples' efficacy, outcome efficacy, use of communal coping, social support for diet and physical activity, COVID-19
Month 18	+/- 14 days from target assessment date	Weight, dietary intake, physical activity, transformation of motivation, couples' efficacy, outcome efficacy, use of communal coping, social support for diet and physical activity, brief pain inventory-short form, weight loss methods, COVID-19
Month 21	+/- 14 days from target assessment date	Transformation of motivation, couples' efficacy, outcome efficacy, use of communal coping, social support for diet and physical activity, COVID-19

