
where *trt* is the treatment indicator and *t* is linear time, then the null hypothesis is  $H_0: \beta_3 = 0$ . In addition, we will tabulate the analysis results for the (fixed) effects of the baseline covariates such as patient sex, patient BMI, and partner BMI.

**Aim 2: Test the hypotheses that average daily caloric intake is significantly lower, and frequency of moderate intensity physical activity is significantly greater, in the partner-assisted arm than the patient-only arm at 24 months.** Dietary adherence will be operationalized as daily intake of calories at months 0, 6, 12, 18, and 24. For each of these same assessment times, physical activity will be summarized as the total and mean minutes of moderate levels per week. Changes in dietary adherence and physical activity will be analyzed using the same methods and models as presented for the Aim 1 analyses of weight loss. Previous experience with these outcomes has shown they are often non-normally distributed; therefore, outcomes may be analyzed as generalized linear mixed models, estimated with adaptive Gaussian quadrature, as needed. As exploratory analyses, we will use the models described for Aims 1 and 2 to examine "spillover" effects(34) of the partner-assisted intervention on partner weight and dietary adherence.(50)

**Aim 3: Assess the extent to which interdependence constructs (transformation of motivation, couple efficacy, outcome efficacy, use of communal coping) mediate the effect of the partner-assisted weight management intervention on weight loss.** We will estimate the extent to which the effect of the partner intervention,  $T_i$  on participants' weight at 6 months,  $Y_i$ , is jointly mediated by a vector of five mediating constructs,  $M_i = (M_{i1}, \dots, M_{i5})$  measured at 3 months: transformation of motivation, couples' efficacy, outcome efficacy, use of communal coping, and social support. Each mediating construct is measured by the summary scale of associated items. We will assess mediation twice: separately for the diet and physical activity domains of the mediators.

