Mediation analysis requires additional assumptions beyond treatment randomization, most importantly: (i) no unobserved mediator-outcome confounders; and (ii) no observed mediator-outcome confounder is affected by the intervention. In order to render assumption (i) more plausible, we will make statistical control for a vector of baseline values,  $B_i$  of the blocking variables, weight, and the mediating constructs, and we will assume that the block of mediators referring to diet and the block referring to physical activity do not affect each other (we do, however, permit that the elements of each  $M_i$  affect each other).

We will follow VanderWeele and Vansteelandt's approach to estimate the natural direct effect (NDE) and the natural indirect effect (NIE) of the intervention relative to a set of mediators,  $M$ , by estimating a set of regression equations.  $E[Y_i | T, M, B] = a_0 + a_1 T_i + a_{21} M_{i1} + \dots + a_{25} M_{i5} + a_3 B_i$

$$E[M_{ik} | T, B] = b_{0k} + b_{1k} T_i + b_{2k} B_i \text{ for } k = 1, \dots, 5.$$

We write  $Y_i(t, M_i(t'))$  for the potential outcome of  $i$  if  $i$  received intervention  $t$  and the value the mediators if  $i$  received intervention  $t'$ . Under assumptions (i), (ii), successful randomization of the intervention (all condition on  $B$ ), and correct functional form, we will then estimate the average natural direct effect of the intervention (versus not) on weight at 6 months as

$$E[Y_i(1, M_i(0)) - Y_i(0, M_i(0))|B] = a_1$$

and the natural indirect (mediation) effect as

$$E[Y_i(0, M_i(0)) - Y_i(0, M_i(1))|B] = b_{11}a_{21} + \dots + b_{15}a_{25}.$$

We will bootstrap the standard errors for the direct and indirect effects.

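### Aim 3 leaves its indirect and direct effects open to avoidable confounding by baseline variables that the trial already collects

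*Combined protocol and SAP*

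**What the plan says.** Section 10.2, Aim 3, estimates how far the effect of the partner intervention on weight at 6 months is carried jointly by five constructs "measured at 3 months: transformation of motivation, couples' efficacy, outcome efficacy, use of communal coping, and social support". It fits one regression of weight on arm, the five mediators and B, and one regression of each mediator on arm and B. The indirect effect is a sum of products of coefficients, and standard errors are bootstrapped.

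The plan names two assumptions beyond randomization as the most important: "i) no unobserved mediator-outcome confounders; and (ii) no observed mediator-outcome confounder is affected by the intervention". On the first it says: "In order to render assumption (i) more plausible, we will make statistical control for a vector of baseline values". The vector B is then defined as the baseline values "of the blocking variables, weight, and the mediating constructs". Identification is stated under these assumptions together with "successful randomization of the intervention (all condition on" B). Section 8.5.1 confirms that the stratification variables (patient sex, patient BMI, partner BMI) enter the models for the "secondary outcomes of diet and physical activity, and mediation analyses". Neither equation contains any other covariate.

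The trial collects much more at baseline. The screening-visit row of Table 7 (Section 9.2.3) begins "Informed consent, medical history/demographics, weight, dietary intake, physical activity, transformation of motivation" and goes on to the pain inventory. The history taken under Section 9.2.1 includes age, heart disease, diabetes and "financial stress, education, smoking status, alcohol use, illicit drug use, employment status, previous weight loss attempts". Table 2 schedules caloric intake, physical activity and pain at month 0. Section 6 classes the mediator question as exploratory.

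**The concern.** Randomization protects the effect of arm on the mediators and of arm on weight. It does not protect the effect of month-3 mediators on month-6 weight, which is an observational association within a trial. The two equations therefore need no confounding of that association given B. The first assumption, as worded, speaks only of unobserved confounders. A variable that is observed but left out of B is covered neither by the assumption nor by the model.

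The omitted variables are plausible common causes. Section 9.2.1 describes coping, confidence and effectiveness items that ask directly about diet and physical activity, so a patient's eating and activity at baseline may shape the month-3 answers as well as month-6 weight. Pain may do the same through activity. These are pre-intervention values, so adjusting for them does not conflict with the second assumption.

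If such a variable matters given B, part of its effect on weight is counted as mediation, or is subtracted from it, and the direct effect absorbs the opposite error. Bootstrapped standard errors would not reveal this. What is at stake is the attribution of the intervention effect to the interdependence constructs, not the intervention effect itself.

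**Working it through.** **The plan's own figures.** The documents give no figure for Aim 3. The sample-size figures for Aim 1 reproduce closely, which supports borrowing their SD and correlation. For a difference of 2.5 kg, SD 19.9 kg, two-sided 5% (sidedness is not stated) and 80% power, a t-test of post scores needs 995 per arm. Multiplying by 2(1 - 0.96) = 0.08 gives 79.6, so 80 per arm and 160 in total. Then 160 x 1.14 = 182.4 (plan: 180), and 180/0.8 = 225 or 183/0.8 = 229 (plan: 230).

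**Inputs from the documents.** SD 19.9 kg and a month 0 to month 24 correlation of 0.96 (Section 10.1). No month-6 figure is given, so the month-24 quantity stands in: change SD 19.9 x sqrt(2 x 0.04) = 5.63 kg, or residual SD given baseline 19.9 x sqrt(1 - 0.96^2) = 5.57 kg.

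**Inputs assumed.** One omitted baseline variable U with the same partial correlation r, given B, with each mediator and with weight; r from 0 to 0.3. The intervention shifts each mediator by 0.5 SD. Mediators are correlated 0.4 to 0.5 with each other. The documents give none of these.

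**One mediator.** With mediator shift b and weight SD s, omitting U biases the indirect effect by b x r x r x s and the direct effect by the same amount with the opposite sign. With b = 0.5 and s = 5.57: 0 kg at r = 0, 0.03 at 0.1, 0.11 at 0.2, 0.25 at 0.3.

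**Five mediators.** With common correlation c, the bias is b x 5 x r^2 x s / (1 + 4c). For b = 0.5, s = 5.63 and c = 0.5:
- r = 0.1: 0.5 x 5 x 0.01 x 5.63 / 3 = 0.05 kg
- r = 0.2: 0.5 x 5 x 0.04 x 5.63 / 3 = 0.19 kg
- r = 0.3: 0.5 x 5 x 0.09 x 5.63 / 3 = 0.42 kg

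**Simulation.** 184 completers (230 x 0.8), five mediators with error correlation 0.4, shift 0.5 SD, no true mediation, true direct effect -1.0 kg, 2,000 runs per row. Both models adjust for baseline weight and baseline mediators.

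| r | Indirect, U omitted | Indirect, U in B | Direct, U omitted | Direct, U in B |
|---|---|---|---|---|
| 0 | 0.01 | 0.01 | -1.03 | -1.04 |
| 0.1 | -0.05 | 0.00 | -0.95 | -1.00 |
| 0.2 | -0.20 | 0.01 | -0.83 | -1.05 |
| 0.3 | -0.45 | -0.01 | -0.59 | -1.02 |

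The sampling SD of the indirect effect was 0.32 to 0.34 kg throughout. The negative sign follows from letting U raise the mediators and lower weight; reversing one of these reverses the bias. With a shift of 0.2 SD the spurious indirect effect is smaller: -0.01, -0.09 and -0.17 kg at r = 0.1, 0.2 and 0.3.

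**Cost in precision.** A further simulation with n = 190 and ten added covariates raised the sampling SD of the indirect effect from 0.315 to 0.333 kg, a ratio of 1.057.

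**The case against.** The plan already takes the main step. Baseline weight, every baseline mediator and the sex and BMI strata are in B, and much of any path from baseline diet, activity or pain to later coping and weight may run through them. The plan claims only to make the assumption more plausible, so it does not contradict itself. The aim is exploratory. At r = 0.2 the bias is smaller than the sampling SD of the estimate, and at r = 0.1 it is negligible. Which covariates to add is partly a matter of judgment, and adding collected ones does nothing about unmeasured confounding.

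Most of this stands, and it rules out stronger readings. A reader might infer that the indirect effect is biased as a matter of fact. The documents contain no association of any omitted variable with the mediators or with weight given B, and the bias is exactly zero if those associations, or the mediator shift, are zero. A reader might also infer that the error would credit the constructs with an effect they lack. The sign is not settled: if patients who are struggling draw more partner support, the bias would run toward the null. Nor should the size be judged against the 2.5 kg design difference, which is a month-24 between-arm target, whereas Aim 3 concerns a month-6 indirect effect.

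The objection does not supply a reason for leaving out pre-intervention variables that are already collected. The precision argument against them is weak, given the small loss shown. Section 18 lists a Statistical Analysis Plan as an attachment, but no separate text of it can be identified here, so further covariate detail there can be neither confirmed nor ruled out.

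**Conclusion.** The point holds as an avoidable exposure to bias, not as a demonstrated bias. The Aim 3 equations need no mediator-outcome confounding given B, and B leaves out plausible common causes that the trial measures before the intervention. The consequence for the indirect and direct effects is equal and opposite, of unknown direction, and between 0 and about 0.4-0.45 kg under the assumed range. At the upper end it exceeds the sampling SD of about 0.3 kg.

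The range rests on assumed correlations, an assumed 0.5 SD shift in all five mediators, and a month-24 SD used for month 6. The total effect, Aims 1 and 2 and the sample size of 230 do not change. The change is worth making because mediation is a stated hypothesis of the trial, and because covariates fixed in advance cannot be chosen later in the light of the results.

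**What to change.** In Section 10.2, Aim 3, extend B in both the weight equation and the mediator equations, for the diet and the activity analyses alike. In addition to the blocking variables, baseline weight and baseline mediators, include:
- at least baseline caloric intake, baseline minutes of moderate activity and baseline pain interference;
- a prespecified set from the collected history: age, education, financial stress, previous weight loss attempts, and history of diabetes or heart disease.

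Use values recorded before the first group session, where assignment is disclosed, and impute missing baseline values so that no patient is lost.

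The cost is one sentence of text, imputation of some baseline values and about 8-10 more coefficients. If the eight strata enter as seven indicators, the weight equation now has 20 coefficients (intercept, arm, five mediators, seven strata, baseline weight, five baseline mediators) and would have 28-30, with 184 to 230 patients. The sampling SD of the indirect effect would rise by roughly 5-6%. No new data are needed. Unmeasured confounding would remain; a short sensitivity analysis for it would be a useful separate addition.

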## 2. Study Summary

[figure not shown]
Title	Using Partners to Enhance Long-term Weight Loss (Partner2Lose)
Short Title and Precis	Partner2Lose
Protocol Number	2018-1400
ClinicalTrials.gov number	NCT03801174
Phase	Phase III equivalent
Methodology	Randomized controlled trial
Study Duration	5 years
Study Center(s)	University of Wisconsin (Madison, WI) Duke University School of Nursing and School of Medicine (Durham, NC) Research Triangle Institute (Seattle, WA)
Objectives	
Aim 1: Test the hypothesis that estimated patient weight is at least 2.5 kg lower at 24 months in the partner-assisted arm than the patient-only arm.
 
Aim 2: Test the hypotheses that estimated daily caloric intake are significantly lower and frequency of moderate intensity physical activity is greater at 24 months in the partner-assisted arm than the patient-only arm.
 
Aim 3: Evaluate whether weight loss is mediated by increases in transformation of motivation, outcome efficacy, couple efficacy, communal coping, and social support for diet and physical activity.

Number of Participants	N=230 couples (460 total)
Diagnosis	Obese/overweight

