Behavioral interventions that involve dietary modification and physical activity, combined with cognitive and behavioral strategies, are efficacious for short-term weight loss but less so for long-term weight loss. Several randomized trials indicate that various dietary approaches (e.g., low-carbohydrate diet, low-fat/low-calorie diet) are efficacious for inducing short-term weight loss.(14, 15) A systematic review indicated that supplementing dietary modification with physical activity improves 12-month outcomes above diet alone.(16) Incorporating behavioral strategies such as self-monitoring, stimulus control, action planning, and problem-solving helps promote adherence to these lifestyle behaviors.(14, 17) Following significant weight loss, most people tend to regain 1-2 kg per year, with the majority of people returning to baseline weight by 5 years.(17) Various strategies have been evaluated to reduce weight regain, including sequential dieting, meal replacements, medications, and behavioral approaches.(18) These strategies have not reduced the overall pattern of regain for most people.(17) Furthermore, research indicates that the best predictor of long-term weight loss is greater initial weight loss.(19) This research suggests that long-term weight loss will be enhanced by 1) identifying efficacious strategies to enhance maintenance and 2) increasing the amount of initial weight loss.

One way to improve long-term weight loss is to increase the effectiveness of social support. Decades of observational research indicates that people with greater social support—often measured by marital status as a proxy—live longer and have better health.(20) Because domestic partners share eating habits, physical activity patterns, and other health behaviors, there are frequent opportunities for partners to provide each other with informational, emotional, and instrumental support.(21) Furthermore, domestic partners are the preferred source of support for most people.(22, 23) Despite the positive effects noted in observational research, trials of weight loss interventions involving spouses/partners have not yielded uniformly positive effects.(24)

[figure not shown]

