Taken together, previous research indicates a possible benefit to including partners in weight loss efforts but underscores the need for rigorous research on efficacy that builds on modern theoretical frameworks. Trials are needed that (1) are rigorous in design and implementation; (2) address weight loss initiation and maintenance; (3) systematically train couples to communicate about health and train partners in strategies for providing effective support for health behavior change; (4) isolate the partner intervention to provide a stringent test; and (5) evaluate theoretically specified mediators. This study accomplishes each of these.

Framing a health problem as “our” problem can initiate communal coping responses to promote health behavior change. The domestic partnership can be leveraged to help initiate and maintain behavior change. According to Lewis’ interdependence model of communal coping and behavior change,(37) couples who approach behavior change as a problem to be tackled together versus independently (referred to as ‘transformation of motivation’) are more likely to utilize effective communal coping processes, including higher levels of (1) outcome efficacy (i.e., a couple’s beliefs about the utility of communal coping for improving health), (2) couple efficacy (i.e., a couple’s confidence that they can engage in communal coping efforts), and (3) use of communal coping strategies (i.e., communicating about and coordinating actions relevant to the health problem, such as joint decision making and planning regarding health behavior and identifying and practicing methods of providing informational, emotional, and instrumental support). Our intervention is designed to affect these interdependence constructs to improve long-term weight loss and associated health behaviors (Figure 1). We will measure these constructs so that we can empirically assess the extent to which they mediate the effect of our partner-assisted intervention on long-term weight loss.

Figure 1. Conceptual Model Based on Interdependence Theory

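### Aim 3 equates its regression coefficients with natural direct and indirect effects on an unchecked assumption that each mediator acts on weight equally in both arms; a sensitivity fit with arm-by-mediator terms would cover this

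*Combined protocol and SAP*

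**What the plan says.** Section 10.2, Aim 3, gives one outcome regression, "E[Y_i | T, M, B] = a_0 + a_1 T_i + a_{21} M_{i1} + \dots + a_{25} M_{i5} + a_3 B_i", and one regression per mediator, "E[M_{ik} | T, B] = b_{0k} + b_{1k} T_i + b_{2k} B_i", for k = 1 to 5. The outcome model contains no product of arm and mediator.

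The direct effect is then set to the arm coefficient: "E[Y_i(1, M_i(0)) - Y_i(0, M_i(0))|B] = a_1". The indirect effect is set to a sum of five products: "E[Y_i(0, M_i(0)) - Y_i(0, M_i(1))|B] = b_{11}a_{21" and so on to the fifth product (the quote stops inside the first).

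These identities are stated subject to no unmeasured mediator-outcome confounding, no mediator-outcome confounder affected by the intervention, successful randomization and correct functional form: "and correct functional form, we will then estimate the average natural direct effect of the intervention (versus not) on weight at 6 months". Standard errors are bootstrapped. The analysis is run twice, for the diet and the physical activity versions of the mediators. Section 6 classes mediation as exploratory.

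**The concern.** A single slope per mediator means that one unit of support, efficacy or coping is assumed to change weight by the same amount in both arms. Section 5.1 gives a reason to ask whether that is so: "One way to improve long-term weight loss is to increase the effectiveness of social support". It also calls for trials that "train partners in strategies for providing effective support for health behavior change". Under Section 9.2.2 only the partner-assisted couples receive this training, and it concerns the manner of support as well as its amount. Some mediators are scored by frequency: Section 9.2.1 measures use of communal coping by how often the couple does things. If training changes what a given frequency achieves, the slope differs by arm.

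Aim 3 asks how much of the effect runs through these constructs. If slopes differ, part of what better support achieves would be reported as direct, and the indirect estimate would match neither of the two indirect effects that can then be defined.

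**Working it through.** **1. The plan's identities under its own model.** With no arm-by-mediator term, Y(1,M(0)) − Y(0,M(0)) = a1, so the direct-effect identity holds. For the indirect effect, Y(0,M(1)) − Y(0,M(0)) = Σ b1k·a2k. The plan prints the difference the other way round, Y(0,M(0)) − Y(0,M(1)), which equals −Σ b1k·a2k. The printed identity therefore has the wrong sign even without interaction. This looks like a slip in the notation; the estimator Σ b1k·a2k is the usual one.

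**2. Allow slopes to differ.** Let mediator k have slope a2k in the patient-only arm and a2k + a4k in the partner-assisted arm. Then:
- direct effect at the comparator mediator level: a1 + Σ a4k·E[Mk(0)|B]
- arm-0 indirect effect: Σ b1k·a2k
- arm-1 indirect effect: Σ b1k·(a2k + a4k)
- total effect: the direct effect plus the arm-1 indirect effect.

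**3. What the additive model returns.** The fitted common slope is a2k + w·a4k, where w is the partner-assisted arm's share of within-arm mediator variance (1/2 under equal allocation and equal variances). Hence:
- additive indirect estimate = arm-0 indirect effect + w·Σ a4k·b1k
- additive direct estimate = direct effect + (1 − w)·Σ a4k·b1k.

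At w = 1/2 the indirect estimate lies midway between the arm-0 and arm-1 versions. The two components still add to the total. If every a4k or every b1k is zero, nothing goes wrong.

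**4. Illustration.** None of these inputs is in the documents. Assumed: each mediator raised by 0.4 SD, comparator slope −0.3 kg per SD on each of five mediators, direct effect −1.00 kg, comparator mediator mean 0, w = 1/2. The arm-0 indirect effect is 5 × 0.4 × (−0.3) = −0.60 kg.

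| | Slope difference −1 kg/SD on one mediator | Slope difference −0.3 kg/SD on all five |
|---|---|---|
| Σ a4k·b1k | −1 × 0.4 = −0.40 | 5 × (−0.3) × 0.4 = −0.60 |
| Arm-1 indirect effect | −0.60 − 0.40 = −1.00 | −0.60 − 0.60 = −1.20 |
| Additive indirect estimate | −0.60 − 0.20 = −0.80 | −0.60 − 0.30 = −0.90 |
| Additive direct estimate | −1.00 − 0.20 = −1.20 | −1.00 − 0.30 = −1.30 |
| Total, true and additive | −2.00 | −2.20 |

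Simulation of 4,000 trials per scenario (200 patients, mediator correlation 0.4, residual SD 4 kg, all assumed) agrees with the table to within about 0.03 kg, and the fit with products recovers the true values to about the same accuracy.

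**5. Unequal variances.** In a second assumed setting (each a1, a2k and a4k = −0.5, b1k = 0.4) the true direct effect is −0.50 and the indirect effects are −1.00 (arm 0) and −2.00 (arm 1). With equal variances the additive model gives −1.00 direct and −1.49 indirect. With the partner-assisted arm's mediator SD at 0.7 times the comparator's it gives −1.18 and −1.33; at 1.4 times, −0.84 and −1.66. The split moves with w, as in step 3.

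**6. Price of the products.** In the step 4 simulation without interaction, both models are unbiased for Σ b1k·a2k. The SD of the indirect estimate is about 0.24 kg for the additive model and about 0.30 kg with products, a ratio of 0.30/0.24 = 1.25.

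**The case against.** The strongest reply is that the documents mostly describe mediation through higher mediator levels, which the additive model captures. Aim 3 in the Study Summary reads: "Evaluate whether weight loss is mediated by increases in transformation of motivation, outcome efficacy, couple efficacy, communal coping, and social support". Section 5.3 reports that support rose in a predecessor trial. The perceived effectiveness of communal coping is itself a measured scale, and outcome efficacy is one of the five mediators, so better support may appear as a higher score and not as a steeper slope. A reader might infer that the rationale contradicts equal slopes. It does not: the sentence on effectiveness in Section 5.1 permits that reading without requiring it. This part of the objection stands.

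It is also fair that the plan discloses correct functional form as a condition, so the direct-effect formula is conditionally valid. What remains is that the condition goes unchecked in the supplied text, whereas Aim 1 tests its own functional form for time with Wald or likelihood ratio tests. A separate Statistical Analysis Plan is listed in Section 18 but was not available, so a check described there cannot be excluded.

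A further objection is that extra models add freedom to an exploratory aim already analyzed in two domains. That stands unless one analysis is named as leading.

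**Conclusion.** The point holds as a low-priority improvement to an exploratory aim. The outcome model lacks arm-by-mediator terms, and its coefficients equal the natural effects only under equal slopes. If slopes differ and levels shift, each component is off by its share of Σ a4k·b1k, unless the terms cancel. The total effect and the primary 24-month comparison are untouched.

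A reader might infer from the illustration that the mediated part will be misreported by a known fraction. The documents do not support that. The slope differences are assumed, and the same additive estimate is 33% to 50% larger than the arm-0 indirect effect (0.20/0.60, 0.30/0.60) and 20% to 25% smaller than the arm-1 effect (0.20/1.00, 0.30/1.20). The shifts of 0.20 to 0.30 kg are about the size of the estimator's own SD in that simulation.

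The reversed sign in the printed indirect contrast is a separate error and depends on no assumption about slopes.

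**What to change.** In Section 10.2, Aim 3:

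- Keep the additive model and name it as the leading analysis.
- Prespecify one sensitivity fit that adds the five products T × Mk, with coefficients a4k. From it report the direct effect at the comparator mediator level, a1 + Σ a4k·E[Mk(0)|B]; the arm-0 indirect effect, Σ b1k·a2k; and the arm-1 indirect effect, Σ b1k·(a2k + a4k). State that only the arm-1 version adds to this direct effect to give the total.
- Use the same bootstrap, show both fits side by side, and do not choose between them by a test of the products.
- Correct the printed indirect contrast to E[Y(0,M(1)) − Y(0,M(0))|B].

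The cost is a few sentences and five more coefficients in each of the two domain analyses. The indirect effects from the second fit will be less precise (about 25% wider in the no-interaction simulation), and there will be more exploratory estimates to present. No additional data are needed.
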